4.2. Exclusion Criteria

Subjects who meet any of the following criteria will be excluded from participation in the study:

- 1. Subject with documented history and/or clinical signs of concomitant presence of an ocular infection caused by viruses (herpes simplex virus [HSV]) or fungi.
- 2. Subject treated with drugs having effects on *Acanthamoeba* cysts prior to study entry, including biguanides (PHMB, chlorhexidine) and diamidines (propamidine, hexamidine).
- 3. Subjects requiring systemic immunosuppression for *Acanthamoeba* associated scleritis.
- 4. Subjects requiring urgent surgical intervention for advanced *Acanthamoeba* keratitis in either eye (e.g., for advanced corneal thinning/melting etc.).

- 5. Subject with known or suspected allergy to biguanides, diamidines or intolerance to any other ingredient of the investigational treatments.
- 6. Subject affected by immunodeficiency diseases or taking systemic immunosuppressive therapy.
- 7. Subject with a major systemic disease or other illness that would, in the opinion of the investigator, compromise subject's safety or interfere with the collection or interpretation of study results.
- 8. If female, pregnancy, planned pregnancy, or breast-feeding.
- 9. Subject is participating in another interventional clinical study with an experimental or unapproved/unlicensed therapy or has participated in another interventional clinical study within 4 weeks prior to this study.

The investigator must ensure that all study enrolment criteria have been met at randomization. If a subject's status changes after randomization, but before the first dose of study drug is given such that he or she no longer meets all eligibility criteria, then the subject should be excluded from participation in the study.

4.3. Concomitant Medication and Other Restrictions during Study

Potential subjects must be willing and able to adhere to the following prohibitions and restrictions during the course of the study to be eligible for participation:

- 1. Female subjects of childbearing potential have to be sexually inactive (abstinent) or have to use an acceptable birth control method as described in Section 4.1 during the study and continuing through 28 days after the last dose of study medication.
- 2. Non-vasectomized male subjects have to use an acceptable birth control method as described in Section 4.1 during the study continuing through 90 days after the last dose of study medication. Female partners should also use an acceptable birth control method as described in Section 4.1 during the study and continuing through 28 days after the last dose of study medication.
- 3. Subjects are allowed to use the following concomitant medications during the study:

Antibiotics: Topical moxifloxacin is permitted for the treatment of intercurrent bacterial infections (unless culture and sensitivity, or clinical progress demands a change). Topical moxifloxacin is not permitted for use as a prophylactic antibiotic in patients with corneal ulcers; PHMB is a good broad spectrum anti-bacterial and an additional antibacterial is not needed for this. The value of prophylaxis is unproven.

Antiviral drugs and antifungal drugs: The use of these drugs is *not* allowed during the study. If subjects are using antiviral or antifungal drugs at study entry, they must be discontinued.

Anti-inflammatory drugs: For subjects on steroids at study entry (already using topical steroids for e.g. mistaken diagnosis of HSV keratitis or as adjunctive treatment for bacterial keratitis), there are the following options:

- a. Either stop steroids, OR maintain, OR reduce the doses (at the investigator's discretion). Unpreserved Dexamethasone (0.1% or 0.15%) is the only topical steroid permitted for use in this trial. Patients using any other topical steroids on trial entry should be changed to this at the appropriate frequency. Diclofenac is the only oral NSAID permitted in the trial and will be ADDED at the appropriate dose (75 mg to 150 mg daily, divided in two or three doses) and continued at any level while topical steroids are in use during the study.
- b. Subjects using topical NSAIDs and ciclosporin at study entry should have these discontinued after randomization.
- c. Subjects using no topical steroids at study entry can have these started together with oral NSAIDs (recommended diclofenac, 75 mg to 150 mg daily, divided in two or three doses) during the study as specified in the schematic overview of the Treatment and Follow-up Protocol.
 - i. Dosing frequency of topical dexamethasone (0.1% or 0.15%): at the discretion of the principal investigator between 1 drop every second day to hourly depending on the degree of inflammation.
 - ii. Dose of diclofenac: at the discretion of the principal investigator. The recommended dosing is 75 mg to 150 mg daily, divided in two or three doses depending on the degree of inflammation

Other permitted topical mediations: Unpreserved lubricants, mydriatics (cyclopentolate, homatropine or atropine) and glaucoma medications are permitted. For glaucoma medications a timolol preparation is recommended as first line (for its low toxicity) and prostaglandin analogues as last resort because of their potential to increase inflammation.

All concomitant medication used in relation to the current eye infection will be reported. For the remaining concomitant medication, only medication in use within 30 days before signing the ICF will be reported in the case report form (CRF). The name of the drug, start and stop date, the indication for use, the total daily dose and route of administration will be recorded. Medications will be coded by standardized dictionary.

4.4. Subject Completion/Withdrawal

Any subject may voluntarily discontinue the study at any time without prejudice. The investigator may elect to discontinue a subject for reasons unrelated to the study drug (e.g. failure to comply with the study protocol, missed visits etc.), for reasons related to the study drug ([serious] adverse event ([S]AE])) or in case of treatment failure. In either event, reason(s) for discontinuation should be recorded on the CRF. Possible reasons for study discontinuation include the following:

Ocular intolerance.

- (S)AEs necessitating discontinuation from the study.
- Treatment failure.
- The subject is lost to follow-up.
- Subject decision not related to an (S)AE.
- Investigator decision (specify).
- Other reason (specify).

Subjects who miss up to 1 full day of treatment within the first 5 days after starting treatment or up to 2 full days of treatment after the first 5 days of treatment should not be discontinued, but will be classified as non-compliant. Subjects will be discontinued from the study if in the opinion of the investigator drug compliance is insufficient.

If the subject discontinues, all the end-of-study visit assessments must be performed, if possible. Moreover, the investigator should ensure (as far as possible) that all used and unused study drug has been collected from the subject. The subject will exit the study and be treated at the investigator's discretion. Discontinued subjects will not be replaced.

Subjects discontinued for (S)AE(s) will be followed-up after subject's discontinuation until the event is resolved or considered medically stable by the investigator. If necessary, the investigator may schedule further visits at his/her discretion. Data collected in the period up to the end-of-study visit will be recorded in the CRF. Data collected after Day 90 following the end of treatment, and related to the (S)AE that led to discontinuation will be recorded in the subject's medical record, and in the sponsor's Safety Database.

In case a subject is lost-to-follow-up, the investigator will attempt to contact the subject (by phone, letter or e-mail) at least twice.

A subject will be considered to have completed the study if all required assessments up to and including the 90 days after end of treatment and end-of-study assessments have been completed.

5. TREATMENTS

5.1. Treatment Assignment

After obtaining oral and written informed consent, subjects meeting the eligibility criteria will be randomized to 1 of the treatment groups in a 1:1 ratio. The randomization schedule will be generated using a computer program and verified for accuracy using strict quality control procedures. Eligible patients will receive a masked treatment assignment with a unique randomization code based on the randomization list. The assigned randomization code will be captured in the electronic Case Report Form (eCRF). This randomization code does not disclose any treatment assignment.

Protocol for bilateral disease: if both eyes are affected, only one eye will be treated with the study treatment and will be considered for the study. This will be the right eye, unless the severity of the infection differs in both eyes, in which case the worst affected eye should be selected. The fellow eye should be treated with the best treatment according to the clinical practice.

Subjects will be assigned to the following treatment groups:

Group 1: 0.08% PHMB + placebo

Group 2: 0.02% PHMB + 0.1% propamidine combination therapy

5.2. Drug dosage and Administration

On Day 0, subjects will receive instructions on how to apply the eye drops. Subjects will receive the assigned treatment to be administered in the affected eye until resolution. Subjects will be treated for a maximum of 1 year after randomization and subjects meeting the criteria for clinical resolution at or before 12 months will be followed up for 90 days before completing the study.

Subjects will receive an initial intensive course of 0.08% PHMB + placebo or 0.02% PHMB + 0.1% propamidine combination therapy.

Treatment throughout the study will be given using 1 drop of each ophthalmic solution in the study eye at different frequencies during the daytime only. At study entry, an intensive 19-day antiamoebic treatment protocol will be initiated as follows:

Day 0 to 5*	1-hourly drops (16 drops in a day) for 5 days
Day 6 to 12	2-hourly drops (8 drops in a day) for 7 days
Day 13 to 19	3-hourly drops (6 drops in a day) for 7 days
Day 20	Then 4x daily thereafter

^{*} on the first day of treatment (after randomization) 16 drops might not be feasible, in this case the treatment should be applied as many times as possible but not exceeding the hourly regimen.

Notes on treatment

- i. The frequency will be maintained at 4x daily unless there is a relapse (see Box XI, Relapse on page 42). In the event of a relapse, culture negative subjects will receive the same intensive 19-day treatment course as given at study entry.
- ii. Antiamoebic drops will be discontinued when clinical resolution is reached (see Figure 2 and Legend IV Discontinue treatment).
- iii. Clinical resolution is a clinical definition, resulting from a slit lamp examination, with the following findings:

- No corneal inflammation (including subepithelial infiltrates, stromal infiltrates and oedema) that requires treatment, with a healed corneal epithelium and minimal punctate staining (10 dots or less equivalent to Grade 1 on the Oxford Scale).
- No or mild conjunctival inflammation (including bulbar injection, bulbar oedema, tarsal hyperemia): mild conjunctival inflammation is acceptable if related to other concurrent conditions such as blepharitis.
- No limbitis, scleritis or anterior chamber inflammation.

For subjects on steroids or oral NSAIDs at study entry (already using topical steroids for e.g. mistaken diagnosis of HSV keratitis or as adjunctive treatment for bacterial keratitis), the same intensive 19-day antiamoebic treatment protocol will be used. For their steroid use there are the following options:

• Either stop steroids, OR maintain, OR reduce the doses (at the investigator's discretion). Unpreserved Dexamethasone (0.1% or 0.15%) is the only topical steroid permitted for use in this trial. Patients using any other topical steroids on trial entry should be changed to this at the appropriate frequency. Diclofenac is the only oral NSAID permitted in the trial and will be ADDED at the appropriate dose (usually 75 mg to 150 mg three times daily) and continued at any level while topical steroids are in use during the study.

Detailed instructions about the use of concomitant medication and adjunctive therapy are given in Section 4.3 "Concomitant medication and other restrictions during study" and also in Section 5.3 "Treatment and Follow up Protocol"

The study drug(s) will be applied to the affected eye. In case both eyes are affected, only 1 eye will be treated with study treatment. This will be the right eye, unless the severity of the infection differs between eyes, in which case the worst affected eye should be selected. The fellow eye should be treated with the best treatment according to the clinical practice.

One drop of 0.1% propamidine or placebo (multiple-use containers) will be administered first, followed after a minimum of 5 minutes by 0.08% or 0.02% PHMB (single-use vials).

The single-use vials should be used immediately after opening and the remaining solution should be discarded. The multiple-use containers should be closed after each use and kept for up to 28 days after opening.

On Day 0, study drugs will be administered after completion of all baseline assessments and randomization. The first application will be done at the clinical research center by the subject under supervision of a member of the study team. Thereafter, study drugs will be applied at home.

Before administration, both single-use vials and the multiple-use containers should be shaken.

If the subject misses a dose of study drug, the subject should wait and take the next dose according to the treatment schedule. Subjects who miss up to 1 full day of treatment within the first 5 days

after starting treatment, or up to 2 full days of treatment after the first 5 days following the start of treatment should not be discontinued, but will be classified as non-compliant. These subjects will be included in the Full Analysis Set and excluded from the analysis of the Per-Protocol Analysis Set (see Section 7.17.1).

The vials and containers should be stored at a temperature lower than 25°C (or at room temperature) and protected from freezing. Research center staff will instruct subjects on how to store study drug for at-home use.

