Anti-inflammatory drugs: For subjects on steroids at study entry (already using topical steroids for e.g. mistaken diagnosis of HSV keratitis or as adjunctive treatment for bacterial keratitis), there are the following options:

- a. Either stop steroids, OR maintain, OR reduce the doses (at the investigator's discretion). Unpreserved Dexamethasone (0.1% or 0.15%) is the only topical steroid permitted for use in this trial. Patients using any other topical steroids on trial entry should be changed to this at the appropriate frequency. Diclofenac is the only oral NSAID permitted in the trial and will be ADDED at the appropriate dose (75 mg to 150 mg daily, divided in two or three doses) and continued at any level while topical steroids are in use during the study.
- b. Subjects using topical NSAIDs and ciclosporin at study entry should have these discontinued after randomization.
- c. Subjects using no topical steroids at study entry can have these started together with oral NSAIDs (recommended diclofenac; 75 mg to 150 mg daily, divided in two or three doses) during the study as specified in the schematic overview of the Treatment and Follow-up Protocol.

Other permitted topical mediations: Unpreserved lubricants, mydriatics (cyclopentolate, homatropine or atropine) and glaucoma medications are permitted.

TREATMENT ASSIGNMENT

Protocol section 5.1 Treatment Assignment, page 38

Randomization to one of the treatment groups will be in a 1:1 ratio. The randomization schedule will be generated using a computer program and verified for accuracy using strict quality control procedures. Eligible patients will receive a masked treatment assignment with a unique randomization code based on the randomization list. The assigned randomization code will be captured in the electronic Case Report Form (eCRF).

Protocol for bilateral disease: if both eyes are affected, only one eye will be treated with the study treatment and will be considered for the study. This will be the right eye, unless the severity of the infection differs in both eyes, in which case the worst affected eye should be selected. The fellow eye should be treated with the best treatment according to clinical practice.

DRUG DOSAGE AND ADMINISTRATION

Protocol section 5.2 Drug dosage and Administration, page 39

On Day 0, subjects will receive instructions on how to apply the eye drops. Subjects will receive the assigned treatment

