- Either stop steroids, OR maintain, OR reduce the doses (at the investigator's discretion). Unpreserved Dexamethasone (0.1% or 0.15%) is the only topical steroid permitted for use in this trial. The frequency of use is at the discretion of the investigator.
- Patients using any other topical steroids on trial entry should be changed to this at the appropriate
 frequency. Diclofenac is the only oral NSAID permitted in the trial and will be ADDED at the dose
 determined by the investigator (75 mg to 150 mg daily, divided in two or three doses) and continued at any
 level while topical steroids are in use during the study.

Subjects using antifungals or antivirals on study entry must discontinue these after randomization.

SCHEMATIC OVERVIEW OF THE TREATMENT AND FOLLOW-UP PERIOD

Protocol section 5.3 Treatment and Follow-up Protocol, page 41

. Legend for Figure 2: Schematic Overview of the Treatment and Follow-up Period

The pathways are **colour coded**:

- Pale blue text boxes and lines for responding disease or treatment success and STUDY END POINT
- Red text boxes and lines for poorly responsive and recurrent / relapsing disease presumed to be due to replication of Acanthamoeba
- Pink text box for exacerbations of inflammation presumed to be due to flare ups of inflammation secondary to the immune response to non-viable *Acanthamoeba*
- Black text boxes for treatment failure endpoints ALL leading to TRIAL EXIT

Each box is labelled with a Roman numeral I to XVIII. The legend below describes the rationale for each step:

I. FOLLOW UP PROTOCOL from day zero at TRIAL ENTRY.

Treatment throughout the study is given using 1 drop of each ophthalmic solution in the study eye at different frequencies during the daytime only:

At trial entry initiate an intensive 19 day anti-amoebic treatment protocol:

Day 0-5: every hour daytime only hourly drops (16 drops a day) for five days.

Day 6-12: 2 hourly (8 drops a day) for 7 days

Day 12-19: 3 hourly (6 drops a day) for 7 days

Day 20: reduce to 4x daily and continue thereafter.

- a. This frequency is maintained at 4x daily unless there is a relapse of infection (XI RELAPSE of infection) when culture negative patients receive the same intensive 19 day treatment course as given at trial entry.
- Anti-amoebic drops are discontinued as when the clinical findings are as described in IV DISCONTINUE TREATMENT.

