a. Either stop steroids, **OR** maintain steroids, **OR** reduce the doses of steroids (at the investigator's discretion). Change steroid therapy to unpreserved topical dexamethasone (0.1% or 0.15%) if not using this already. When steroid is to be continued at any level; ADD an oral non-steroidal anti-inflammatory drug

(NSAID). The oral NSAID used in the trial is diclofenac; change therapy to diclofenac if patient is on alternative NSAID at study entry.

Dexamethasone (0.1% or 0.15%) drops and oral diclofenac are permitted in the study and may be discontinued, tapered or continued on inclusion into the study at the discretion of the investigator:

- Dosing frequency of topical dexamethasone (0.1% or 0.15%): between 1 drop every second day to hourly depending on the degree of inflammation.
- Dose of diclofenac: The recommended dosing is 75 mg to 150 mg daily, divided in two or three doses depending on the degree of inflammation

For subjects using antifungals or antivirals on study entry: discontinue antifungals or antivirals.

For subjects using topical antibiotics on study entry for concurrent bacterial keratitis: alter antibiotic to moxifloxacin unless there is evidence from microbiology studies that the bacteria are resistant to moxifloxacin.

Prophylactic antibiotics for patients with ulceration: discontinue prophylactic antibiotics.

Other permitted topical mediations: Unpreserved lubricants, mydriatics (cyclopentolate, homatropine or atropine) and glaucoma medications are permitted. For glaucoma medications a timolol preparation is recommended as first line (for its low toxicity) and prostaglandin analogues as last resort because of their potential to increase inflammation.

After the 20 day treatment in Box I patients will either stabilize or improve and move to the treatment pathway in Box II or deteriorate and move to the pathway in Box VIII.

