5.3.2. Poor Response at 3 weeks or Treatment Failure

BOX VIII POOR RESPONSE at 3 weeks.

Poor response at 3 weeks from I Trial entry or XIII RESTART: patients are managed using the guidelines in IX. Criteria for this include enlarging ulcer, stromal thinning, deteriorating corneal, inflammation (infiltrate including ring abscess), intraocular inflammation (uveitis and hypopyon) and/or scleritis.

BOX IX INTRODUCE ANTI-INFLAMMATORY TREATMENT

- a. For subjects NOT using topical steroids start these WITH oral NSAIDs. The topical steroid that is permitted in the Trial is unpreserved dexamethasone (0.1% or 0.15%). The oral NSAID used in the trial is diclofenac. The frequency of the drops and the dose of oral NSAID that is used is at the discretion of the Investigator.
- b. For subjects already on unpreserved topical dexamethasone (0.1% or 0.15%) and oral diclofenac, increase the frequency of the steroid drops and dosage of oral diclofenac when possible.

This is expected to result in an improvement for most cases and they move to BOX II.1 STABLE or BOX III IMPROVEMENT.

BOX X CONTINUED DETERIORATION

Alternatively, if continued deterioration occurs, cases move to Box XVIII - TREATMENT FAILURE and EXIT Trial.

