7.10.3 Clinical laboratory

Haematology, biochemistry and urinalysis are collected at the baseline and end-of-study visits only. For the purpose of summary tables on laboratory test results, any value reported as below the lower limit of quantification or as undetectable will be considered as missing, and any value reported as above the upper limit of quantification will be considered as being equal to the upper limit. In data listings, the reported value will be presented.

For continuous laboratory parameters, summary statistics on the laboratory test results will be presented by visit. For the end-of-study visit, summary statistics on the change from baseline will also be presented.

For categorical laboratory parameters, frequency tables on the laboratory test results will be presented by visit. For the end-of-study visits, the shift from baseline will also be presented.

For all laboratory parameters, frequency tables on the clinical interpretation of the laboratory test results (*e.g.* normal, abnormal but not clinically significant, abnormal and clinically significant) will be presented by visit. For the end-of-study visit, the shift from baseline will also be presented.

Each parameter will be presented in a separate table. A list of all laboratory parameters (including specification of the standardised units to be used for analysis) is presented below:

LINK Medical Study ID: PSR012

Clinical laboratory tests will be presented with summary statistics. In addition, the tests will be analysed with ANCOVA (baseline value of respective laboratory test will be included in the model).

All results will be regarded as descriptive only. The p-values will be used to flag safety and tolerability variables worthy of further attention.

Null hypothesis:

• No difference between test treatment and reference treatment

Clinical laboratory tests conducted at planned visits for which laboratory sampling was not planned, as well as unplanned visits with laboratory sampling that are reported through the eCRF, will be included in the listings and, if deemed necessary, commented in the Statistical report.

Laboratory class	Parameter*	Unit**
Haematology	Total red blood cell count	x10^12/L; x10^6/microlitre
	White blood cell count	x10^9/L; x10^3/microlitre; /microlitre
	Neutrophils	x10^9/L; %; /microlitre
	Lymphocytes	x10^9/L; %; /microlitre
	Monocytes	x10^9/L; %; /microlitre
	Eosinophils	x10^9/L; %; /microlitre
	Basophils	x10^9/L; %; /microlitre
	Haematocrit	L/L; %

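### Protocol section 5.2 sets oral diclofenac at 225–450 mg/day, three times the 75–150 mg/day given at every other place that states a dose

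*Protocol*

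**What the plan says.** Protocol section 5.2 covers subjects who enter on steroids or oral NSAIDs. It names diclofenac as the only oral NSAID allowed and says it "will be ADDED at the appropriate dose (usually 75 mg to 150 mg three times daily", to continue for as long as topical steroids are in use. A following paragraph adds: "Detailed instructions about the use of concomitant medication and adjunctive therapy are given in Section 4.3", and also points to section 5.3.

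The Synopsis counterpart of that text, under Drug Dosage and Administration, sets the dose as "determined by the investigator (75 mg to 150 mg daily, divided in two or three doses". The Synopsis section on concomitant and previous medications and Protocol section 4.3 use nearly the same sentence as section 5.2, but with the daily total: "will be ADDED at the appropriate dose (75 mg to 150 mg daily, divided in two or three doses". Section 5.3, Box I, agrees: "The recommended dosing is 75 mg to 150 mg daily, divided in two or three doses".

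Box IX (section 5.3.2) gives no figure. It leaves the NSAID dose to the investigator and, for poor responders already on both drugs, says to "increase the frequency of the steroid drops and dosage of oral diclofenac when possible". The SAP gives no diclofenac dose.

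**The concern.** One instruction appears with two incompatible doses, and the higher one stands in the section whose title announces drug dosage and administration. A site could reasonably look there first, find a number and read no further. The section refers to 4.3 and 5.3 for detail but does not say that they prevail.

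At stake is systemic NSAID exposure in subjects of either arm, for as long as topical steroids continue within a treatment period of up to one year. Subjects are eligible from age 12, with those under 18 at selected sites only. No laboratory test is scheduled during treatment; SAP section 7.10.3 states: "Haematology, biochemistry and urinalysis are collected at the baseline and end-of-study visits only".

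**Working it through.** **Inputs: every numeric statement of the diclofenac dose in the Protocol**

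| Place | Dose as stated | Daily total |
|---|---|---|
| Section 5.2 | 75–150 mg, three times a day | 225–450 mg |
| Synopsis, Concomitant and Previous Medications, item a | daily total, 2 or 3 doses | 75–150 mg |
| Same, item c | daily total, 2 or 3 doses | 75–150 mg |
| Synopsis, Drug Dosage and Administration | daily total, 2 or 3 doses | 75–150 mg |
| Section 4.3, item 3a | daily total, 2 or 3 doses | 75–150 mg |
| Section 4.3, item 3c | daily total, 2 or 3 doses | 75–150 mg |
| Section 4.3, item 3c.ii | daily total, 2 or 3 doses | 75–150 mg |
| Section 5.3, Box I | daily total, 2 or 3 doses | 75–150 mg |

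That is seven statements against one.

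**Daily total under section 5.2** = dose per administration × administrations per day

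- Low end: 75 × 3 = 225 mg/day
- High end: 150 × 3 = 450 mg/day

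**Comparison with the other seven**

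- Ratio at matching ends: 225/75 = 3 and 450/150 = 3
- Excess at matching ends: 225 − 75 = 150 mg/day and 450 − 150 = 300 mg/day
- Gap between the ranges: 225 − 150 = 75 mg/day, with 225/150 = 1.5

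The gap is positive, so no dose satisfies both instructions.

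**Per-dose amounts under the other seven**

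- Twice a day: 75/2 = 37.5 mg to 150/2 = 75 mg
- Three times a day: 75/3 = 25 mg to 150/3 = 50 mg

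Section 5.2 thus appears to have used the daily range as the amount per dose.

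**The case against.** The strongest reply is that section 5.2 does not mandate a dose. It calls the figure the *usual* one and asks for an appropriate dose. Sections 4.3 and 5.3 leave the dose to the investigator, and section 5.2 itself sends the reader there for detail. Both sections agree with each other and with the Synopsis, so the intended dose is easy to infer. This lowers the chance of misdosing. It does not settle which dose governs, and *usually* presents 225–450 mg/day as the norm.

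Four further points limit the reach of the problem:

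- **Exposed group.** The line applies only to subjects on steroids or oral NSAIDs at entry. The investigator may stop the steroid, and under section 5.3, Box I, the NSAID is added when steroid is continued. The documents do not say how many subjects this leaves.
- **Monitoring.** The Schedule of Assessments reviews concomitant therapy and adverse events at every visit, so a high dose could be noticed there. SAP section 7.10.3 also allows for laboratory samples taken outside the plan. Only scheduled laboratory checks are absent during treatment.
- **Young subjects.** A footnote in SAP section 7.9.3 mentions one subject, aged 15, on the youth EQ-5D, which the Protocol assigns to those aged 15 or under. This suggests few young adolescents were enrolled. It does not count those aged 16 or 17.
- **Harm.** The documents give no labelled maximum and no toxicity data for diclofenac, so the clinical danger of 225–450 mg/day cannot be judged from them.

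The missing ceiling for increases under Box IX is a separate, lesser matter. That instruction is qualified by feasibility, and several statements of the range could be read as already setting 150 mg/day as the limit.

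All of this bears on likelihood and severity. None of it reconciles the two doses.

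**Conclusion.** The contradiction stands. Section 5.2 gives a daily diclofenac dose three times that of the seven other numeric statements, 150 to 300 mg/day more at matching ends, with no overlap. Reading it as a drafting error rather than a second intended regimen is an inference, but a strong one: the Synopsis counterpart and the near-identical sentence in section 4.3 both carry the daily total.

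It should be fixed as a matter of subject safety and internal consistency. It does not touch the sample size or the primary analysis, and no difference between arms is claimed. Nothing in the documents shows that any subject received more than 150 mg/day. The conclusion needs no outside figure for a maximum diclofenac dose.

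**What to change.** 1. **Text.** Once the sponsor's medical lead confirms the intended dose, replace the parenthesis in section 5.2 with the daily-total wording already used in section 4.3 (75–150 mg per day in two or three divided doses). Add to the cross-reference that the section 4.3 dose governs.
2. **Optional.** State whether 150 mg/day is the ceiling for increases under Box IX.
3. **Sites.** Send a short letter to any site with subjects still on treatment.
4. **Look-back.** List total daily diclofenac dose by site and arm, flag any record above 150 mg/day, and review adverse events and end-of-study laboratory values in the flagged subjects. Section 4.3 already requires, for medication related to the eye infection, that "the total daily dose and route of administration will be recorded". The planned summaries in SAP section 7.7 are by therapeutic subgroup and preferred name, so they would not show dose.

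SAP section 5.2, in a document signed in July 2021, describes randomisation in the past tense. If no subject is still on treatment, the look-back is the part that remains useful.

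The cost is one parenthesis, one or two clauses, one letter, and one listing with review of any flagged subjects. No new data are collected.
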